#### **6.3.4 Blood Draw Procedures**

For the blood draws, the subject will be comfortably seated and identification of the subject will be confirmed. Blood will be drawn from the median cubital vein. Initially a tourniquet will be placed on the arm, proximal to the location where the blood will be drawn. The skin around this area will be wiped with an alcohol swab (or iodine prep). A needle will be inserted, bevel facing upwards, into the median cubital vein. Once the needle is in the vein, a vacutainer is pushed onto the needle holder and this will be repeated until all blood samples required are completed. Once the needle is removed, clean cotton wool will be pressed onto the wound. The tubes will be labeled immediately. Sufficient blood will be drawn to permit a chemistry panel with electrolytes and CBC. Hemoglobin and hematocrit counts, serum potassium and uric acid, liver function (alanine aminotransferase (ALT), aspartate aminotransferase (AST) and alkaline phosphatase), renal function (blood urea nitrogen [BUN] and serum creatinine), creatine phosphokinase (CPK) to assess muscle injury, and pregnancy in women (human chorionic gonadotropin (hCG)) will be assessed.

### **6.3 Study drug procedures**

Following randomization, subjects will begin a closed label course of 50mg of losartan daily for 4 weeks or placebo for the same duration of time. Losartan will be initiated within 7 days of injury after initial testing has been performed and any abnormalities are ruled out. No initial dosage adjustment is necessary. The drug is self-administered with or without food and will be ingested once a day.

Prior to starting the study medication, a study physician will review the effects of Losartan, its side-effects and how the medication should be taken with all subjects. At this time, the physician will answer any questions the subject has regarding the study medication.

The UPMC Investigational Drug Service will provide the Losartan or placebo. The placebo will be formulated to have the same appearance as the Losartan. Study medications will be provided to the subjects free of charge. Subjects will be evaluated weekly while they are taking the medication. Blood work will be repeated 2, 4, and 6 weeks after randomization.

During the weekly patient encounters, a member of the research team will answer any questions the subject might have about the medication, will assess and promote medication adherence and monitor any side effects that the patient

might be experiencing. Also, the subject will be instructed to bring the medication to each visit so that pill counting can be performed as a measure to assess adherence. At each weekly encounter with the study staff, the subject will be given a medication log to complete. The medication log will allow the patient to record the times/days the study medication and any concomitant medications taken during that time period.

## **6.4 Follow-up procedures** *(Incorporate only if follow-up procedures will be performed)*

### **6.4.1 Standard of Care Rehabilitation**

All subjects will undergo a standardized post-injury rehabilitation program, supervised by a physical therapist or athletic trainer. The rehabilitation protocol will be similar to that described by Sherry. The rehabilitation will be divided into 2 phases. The initial phase will focus on static stretching, isometric hamstring exercises and active range of motion. This will include 10 minutes of low-intensity cycling on a stationary ergometer with no resistance, static supine and long-sit hamstring stretching exercises (30 second hold, 4 repetitions each), submaximal isometric hamstring contractions at 20° and 90° of knee flexion (10 second hold, 10 repetitions at each angle) and prone knee flexion without resistance (30 repetitions). Ice will be applied at the end of the exercise session for 20 minutes. The phase 1 exercise program will be performed daily.

Subjects will progress to phase 2 when they can walk with the same stride length and stance time on the injured and un-injured legs and can do a high knee march in place without pain. In phase 2, the focus will be on dynamic stretching and concentric and eccentric hamstring strengthening. Subjects will ride a stationary ergometer for 15 minutes with a moderate level of resistance, during which the subject shoulder perceive a moderate level of exertion (12-13 on Borg scale of perceived exertion). This will be followed with standing, supine and long-sit dynamic hamstring stretching exercises. Prone leg curls will be performed to strengthen the hamstring muscles using a daily adjustable progressive resistance exercise (DAPRE) method as describe by Knight. In this method, subjects will perform 4 sets of resisted hamstring exercises against variable levels of resistance and repetitions as described in the table below (**Table 2**). The number of repetitions completed in the 3rd set will be utilized to determine the amount of weight used for the 4th set and the number of repetitions performed in the 4th set will determine the working weight for the next exercise session (**Table 3**). The “foot catch exercise” will be performed in the standing position. In this exercise, subjects will simulate the swing phase of walking or running as they quickly contract the quadriceps and catch or stop the lower leg before reaching terminal knee extension using an eccentric hamstring contraction. During phase 2, subjects will be permitted to run and jog without high-speed maneuvers as tolerated by pain. Ice will be applied at the end of the exercise session for 20

minutes. Except for the prone leg curls, which will be performed every other day, the phase 2 exercise program will be performed daily.

**Table 2 – Sets, Weight and Number of Repetitions for DAPRE Program**

Set	Portion of Working Weight Used	Number of Repetitions
1	50%	10
2	75%	6
3	100%	As many as possible
4	Adjusted based on number of repetitions in 3 rd set	As many as possible

Subjects will be permitted to begin high-speed running and agility drills when: 1) they have no palpable tenderness in the posterior thigh, 2) hamstring flexibility is within 3° of the un-injured leg and 3) resisted hamstring strength is 85% of the un-injured leg. Subjects will be permitted to return to full practice or military activity when they can tolerate high-speed running and agility drills for 3 consecutive days with no exacerbation of symptoms and when they can perform a 40-yard sprint with no posterior thigh tightness or twinges. Upon return to sports, subjects will be encouraged to continue with the rehabilitation program 3 days a week for at least 2 months after returning to sports.

To ensure consistency in the rehabilitation program for all subject, we will create educational training materials (video and written instructions) demonstrating the correct performance and progression of the rehabilitation program. This information will be distributed to all physical therapists and athletic trainers responsible for rehabilitation of the subjects participating in this study.

Compliance with the rehabilitation program will be assessed by reviewing the physical therapy or athletic training rehabilitation records. Additionally, subjects will independently track exercise compliance by recording the rehabilitation tasks that are performed on a daily basis in an exercise log. This log will be reviewed at each follow-up visit to ensure compliance with the rehabilitation program. To control for co-interventions, applications of heat and ultrasound and use of

**Table 3 – Change in Working Weight for Fourth Set and Next Session Based Upon Number of Repetitions Performed**

Number of Repetitions Performed During Third Set	Fourth Set	Next Session
0-2	Decrease 5-10 lbs.	No change
3-4	Decrease 0-5 lbs.	Increase 5 lbs.
5-7	No change	Increase 5-10 lbs.
8-12	Increase 5-10 lbs.	Increase 10-15 lbs.
> 13	Increase 10-15 lbs.	Increase 15-20 lbs.

neuromuscular electrical will be avoided.

## **6.4.2 Outcome Measures**

The outcomes measures will be collected at the time of study enrolment and at the 1, 2, 3, 4 and 6 weeks and 3, 4, 6, 9 and 12 month follow-up as described in **Table 1** above, using procedures described in a Manual of Operations and Procedures. We will use a **trained** Clinical Research Assistant at each site, who has a background as a physical therapist or athletic trainer, to collect the measures of hamstring flexibility and strength and to conduct all follow-up telephone calls. Prior to data collection, co-I [name] (who has greater than 30 years of experience with collection of clinical outcomes data) will train the Clinical Research Assistants.

A musculoskeletal radiologist will read and interpret the MRI scans to determine the presence and extent of fibrosis and muscle atrophy. A bilateral magnetic resonance imaging (MRI) of both thighs will be conducted. The amount of fibrosis atrophy will be determined from the MRI using MIPAV software (Medical Imaging Processing, Analysis and Visualization, NIH, Bethesda, MD).

All individuals responsible for collecting outcome measures will be blinded to the subject's group assignment throughout the duration of the study.

### **6.4.2.1 Return to Previous Level of Sports Activity and Recurrence of Injury (Specific Aims 3 and 4)**

The primary outcome for return to sports will be the number of days from injury to full, unrestricted return to practice or military training. The secondary outcome for level of sports activity will be the Marx Activity Scale Score. At 4 and 6 weeks, the Marx Sports Activity Scale will be modified to measure sports activity in the last week and at 4, 6 and 12 months the scale will be modified to measure sports activity in the past month.

Recurrence of injury will be monitored over the course of 12 months after study enrolment and randomization. A subject will be considered to have a recurrent injury if there was a specific mechanism of injury that caused a return of posterior thigh pain, tenderness to palpation along the muscle-tendon unit, pain with resisted knee flexion and the inability to participate in sports activities. Recurrent injuries will be monitored weekly during the course of rehabilitation and at each follow-up study visit (1, 2, 3, 4 & 6 weeks, 6 months) and follow-up phone call (3, 4, 9 and 12 months). After return to sports participation, any subject experiencing a recurrent injury will be instructed to contact the Project Coordinator and a return visit will be scheduled to confirm the presence and severity of re-injury.

### **6.4.2.2 Function and Structure of Hamstring Muscle (Specific Aim 2)**

**Pain** – An 11 point (0 to 10) numeric pain rating scale will be used to rate pain at rest and walking at the time of study enrolment and at 1, 2, 3, 4 and 6 weeks after enrolment. Pain with jogging and sprinting will be rated starting when these activities are initiated through the remainder of the in-person and telephone

follow-up visits. The numerical pain rating scale is anchored so that 0 corresponds with no pain and 10 corresponds with worst imaginable pain. The psychometric properties of the numeric pain rating scale compare favorably to other pain rating scales and are the preferred method of rating pain by young and old individuals in a study of experimentally induced pain.

**Measurement of Hamstring Flexibility** – Hamstring length will be assessed by measuring the popliteal angle as described by ten Berge et al. This will be performed by placing the ipsilateral hip at 90° of flexion and passively extending the knee to the end range of motion. To eliminate the possibility of initial muscle stiffness, the knee will be moved to end range extension 3 times before taking the measurement. A standard goniometer will be used to measure the angle of knee flexion. The proximal arm of the goniometer will be aligned with the lateral midline of the thigh on a line between the lateral epicondyle and the center of the greater trochanter of the femur and the distal arm will be positioned parallel to the lateral midline of the leg on a line between the lateral malleolus and lateral epicondyle of the femur. To account for variability between subjects, hamstring flexibility will be expressed as the difference in popliteal angle between the hamstring-injured and contra-lateral normal leg. Using this methodology, ten Berge et al demonstrated adequate levels of intra- and inter-observer reliability (ICC=.82 and .72 respectively) in healthy subjects between 20 and 29 years of age.

**Isometric Hamstring Strength** – A Lafayette hand-held dynamometer (Lafayette Instrument Company, Lafayette IN) will be used to measure isometric hamstring strength at the time of study enrolment and at 1, 2, 3, 4, and 6 weeks after enrolment. For these measurements, the subject will be positioned in the prone position. The dynamometer will be placed on the distal leg approximately 2 cm proximal to the level of the lateral malleolus. The distance from the point of application of the hand-held dynamometer to the lateral joint line will be recorded in centimeters. The amount of force generated by the subject will be resisted by the examiner (i.e. a “make test” will be performed). The test will be performed at 30° and 90° of knee flexion, first on the un-injured leg than on the injured leg. To calculate torque, the force will be multiplied times the distance from the point of application of the hand-held dynamometer to the lateral joint line of the knee. Isometric strength (Newton-meters) of the involved hamstrings will be expressed as an absolute number and as a percentage of strength of the un-injured leg. Trudelle-Jackson et al demonstrated high levels of intra- (ICC ranging from .97-.98) and inter-day (ICC ranging from .85-.87) reliability when using a hand-held dynamometer to test hamstring strength in healthy subjects. Additionally, measurements with the hand-held dynamometer were strongly related to concurrent measurements of isometric strength on an isokinetic dynamometer ( $r$  from 0.83 - 0.85).

**Isokinetic Hamstring Strength** – Isokinetic hamstring strength at 60 and 180° per second will be measured on the Biodex isokinetic dynamometer (Biodex Medical Systems, Shirley NY) 4 and 6 weeks after study enrolment as well as at

the 6 month follow-up visit. Prior to performing the test, the subject will ride a stationary ergometer for 5 minutes at a moderate intensity level and will perform static hamstring stretching exercises (30 second hold, 4 repetitions) for each leg. The subject will be seated on the isokinetic dynamometer so that the axis of rotation of the dynamometer is aligned with the lateral epicondyle of the femur. The length of the input arm will be adjusted so that the pad is positioned just above the lateral malleolus. The dynamometer settings will be recorded to ensure consistency during subsequent testing sessions. To familiarize the subject with the testing protocol prior to performing the maximal effort tests, the subject will perform 2 sub-maximal contractions and 1 maximal contraction at 60°/sec and 6 sub-maximal and 3 maximal contractions at 180°/sec. For the test that is recorded, the subject will perform 3 maximal concentric quadriceps and hamstring contractions at 60°/sec and 20 maximal concentric quadriceps and hamstring contractions at 180°/sec. Verbal encouragement will be provided during testing to ensure maximal effort.

The primary outcome variable of interest will be the involved to un-involved ratio of hamstring peak torque at 60°/sec. Secondary isokinetic variables that will be evaluated include the involved to un-involved ratio of total hamstring work at 60°, the involved hamstring to quadriceps ratio in peak torque at 60°/sec, peak torque and total work at 180°/sec and the ratio of work in the last 3 repetitions to work in the first 3 repetitions at 180°/sec. Pincivero et al demonstrated high levels of test re-test reliability (ICCs ranging from ) over a 7 day period in normal healthy subjects using the Bidex System 2 Isokinetic Dynamometer and a testing protocol similar to that which we will be using.

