**Specific Aim #2: Recovery of Hamstring Muscle Function and Structure**

The primary endpoints to assess hamstring muscle function are the injured to contra-lateral leg differences in the popliteal angle at 6 weeks and 6 months and the injured to contra-lateral ratio of peak isokinetic hamstring torque at 6 weeks and 6 months.

The primary endpoint to assess hamstring structure will be the length and volume of fibrosis within the hamstrings at 6 months as evidence on 3 Tesla MRI.

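### The protocol specifies no repeat readings for the popliteal angle, so a primary side-to-side endpoint may carry reading error that simple averaging would modestly reduce

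*Combined protocol and SAP*

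**What the plan says.** Section 6.4.2.2 measures hamstring length as the popliteal angle. To remove initial stiffness, "the knee will be moved to end range extension 3 times before taking the measurement". Then "A standard goniometer will be used to measure the angle of knee flexion". The outcome is relative to the other leg: "hamstring flexibility will be expressed as the difference in popliteal angle between the hamstring-injured and contra-lateral normal leg". The protocol states that earlier work with this method "demonstrated adequate levels of intra- and inter-observer reliability (ICC=.82 and .72 respectively) in healthy subjects between 20 and 29 years of age".

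Section 9.1.1 lists among the primary endpoints for muscle function "the injured to contra-lateral leg differences in the popliteal angle at 6 weeks and 6 months".

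Neither section says how many readings are recorded per leg or how several would be combined. For isokinetic strength, by contrast, section 6.4.2.2 separates practice contractions from the recorded ones and counts both. Section 6.4.2 adds that outcomes are collected "using procedures described in a Manual of Operations and Procedures"; that manual is not among the documents reviewed. The measurements are made by one trained "Clinical Research Assistant at each site, who has a background as a physical therapist or athletic trainer".

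**The concern.** The three movements to end range are conditioning, not recorded replicates. The reliability figures cited in support are for the angle itself, whereas the endpoint is a difference between two angles, and the plan does not consider the reliability of that difference. Taking a difference helps only so far as the two legs share true variation. That same sharing removes signal variance from the endpoint, while independent reading errors from both legs remain and add.

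This matters because of what the trial is for. Section 9.2 gives 20 subjects (10 per group), concedes that power is insufficient, and says that the aim is to estimate effect sizes for planning later trials. Reading error that could have been averaged out widens the interval around the effect estimate and lowers the standardised effect. With the sample size fixed, better measurement is one of the few ways left to gain precision.

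**Working it through.** **Figure to reproduce.** None. The sample size is given as approved, and the plan states no SD, effect size, alpha or power for this endpoint. The check therefore works in relative units.

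**Input from the documents.** Intra-observer ICC of 0.82 (section 6.4.2.2).

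**Assumptions not in the documents.**
- The ICC of 0.82 applies to single readings.
- Reading errors are independent between legs and between repeats.
- Both legs have the same variance, scaled to 1.
- The true between-leg correlation r is 0, 0.5 or 0.8.
- One reading per leg (k = 1) is the reference case.

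**Step 1: error in the difference.** Error variance for one leg is 1 − 0.82 = 0.18. For the difference it is 2 × 0.18 = 0.36, which is double. The error SD rises by √2 = 1.41.

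**Step 2: variance and reliability of the difference.**
- True variance: 2 × 0.82 × (1 − r)
- Total variance with k averaged readings: 2 × 0.82 × (1 − r) + 0.36/k
- Reliability: true variance divided by total variance

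At r = 0.5 and k = 1, true variance is 0.82, total is 0.82 + 0.36 = 1.18, and reliability is 0.82/1.18 = 0.69.

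**Step 3: three readings per leg.** If all error arises within the session, the error term falls from 0.36 to 0.12, a drop of 0.24. If only half does, it becomes 2 × (0.09 + 0.09/3) = 0.24, a drop of 0.12.

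| r | Variance, k = 1 | Variance, k = 3 | Cut, all error within session | Cut, half within session | Reliability, k = 1 to k = 3 |
|---|---|---|---|---|---|
| 0 | 2.00 | 1.76 | 12% | 6% | 0.82 to 0.93 |
| 0.5 | 1.18 | 0.94 | 20% | 10% | 0.69 to 0.87 |
| 0.8 | 0.688 | 0.448 | 35% | 17% | 0.48 to 0.73 |

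**Step 4: SD scale.** Taking square roots of the variance ratios, the endpoint SD falls by about 6%, 11% and 19% in the three rows if all error is within-session, and by about 3%, 5% and 9% if half is.

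**Why 0.72 is not used.** That figure is the inter-observer ICC. Repeat readings by the same assistant do not remove between-observer error, and an offset that one assistant applies to both legs cancels in the difference.

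**The case against.** Several points on the other side are sound, and they limit the size of the gain.

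- **One reading is not stated.** A reader might infer that the plan takes exactly one reading per leg. The singular wording suggests it, but no number is given and the manual may set replicates. The isometric strength text also gives no trial count, which fits such detail being left to the manual. What can be said is that the protocol specifies no replicates.
- **Type of ICC.** The documents do not say whether 0.82 refers to single or averaged readings, or to repeats within or between sessions. If it already reflects averaged readings, the table does not apply.
- **Population.** The ICC comes from healthy subjects. Here one leg has a grade II or III strain, so the true deficit will vary between subjects. That would lower the between-leg correlation and move the answer towards the top row.
- **Independence.** An assistant who has seen the first reading may repeat it, and averaging then gains less.
- **Small next to other uncertainty.** With 18 degrees of freedom and normal data, the 95% interval for an SD runs from about 0.76 to 1.48 times the estimate, which swamps a change of 5% to 15%. Flexibility is also measured at seven visits (section 3.1, Table 1), and the mixed models in section 9.4 may recover some precision.
- **Not a wrong SD.** A reader might infer that the planning SD would be biased. If the next trial measures in the same way, the SD is the right one for it.

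These points shrink the benefit without reversing it. Under the stated assumptions, averaging cannot make the endpoint noisier, and the change costs little.

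**Conclusion.** The point holds as a cheap improvement. The protocol text specifies no replicate readings for a primary endpoint formed as a difference, and that difference is less reliable than a single leg unless the legs are uncorrelated. Averaging three readings would cut its variance by about 12% to 35% if all error is within-session, or 6% to 17% if half is. This rests on a single-reading ICC of 0.82, independent errors, equal variances and a correlation between 0 and 0.8. The effect is a modest loss of precision, not bias, and nothing in the plan contradicts itself here.

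Two stronger readings are not supported:

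- A reader might convert the gain into 26% to 54% more subjects (1.18/0.94 and 0.688/0.448). Those ratios need the higher correlations and wholly within-session error. At correlation 0 with half of the error within-session, the figure is 2.00/1.88, or 6%.
- A reader might conclude that the noise undermines the 3° flexibility criterion in section 6.4.1. The documents give no SD in degrees and do not say that this check uses the research reading.

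**What to change.** In section 6.4.2.2, add that after the three conditioning movements the same assistant takes three readings per leg, repositioning the goniometer each time. All three are recorded, and the mean is used for the popliteal-angle difference, at least at the 6-week and 6-month primary endpoint visits. If the Manual of Operations and Procedures already requires this, bring the protocol text into line with it. Keeping the individual readings would also let the trial report within-session reliability in its own injured subjects.

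The cost is about a minute per leg, four extra CRF values per visit (six readings instead of two across both legs), and slightly more passive end-range movement of the injured leg.
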